7.1.1.3. Population of Interest

The secondary efficacy analysis of ORR will be based on the All Treated population, unless otherwise specified.

7.1.1.4. Statistical Analyses / Methods

Details of the planned displays are provided in [Appendix 11: List of Data Displays](#) and will be based on GSK data standards and statistical principles.

Unless otherwise specified, endpoints / variables defined in Section [7.1.1.1](#) will be summarised using descriptive statistics, graphically presented (where appropriate) and listed.

7.1.2. Exploratory Efficacy Analyses

7.1.2.1. Endpoint / Variables

MRD Negativity Rate

Minimal Residual Disease (MRD) negativity rate, defined as the percentage of participants who are MRD negative (with threshold 10^{-5}) and achieve confirmed VGPR or CR from treatment start date until disease progression or initiation of new anti-cancer therapy, whichever is earlier, as assessed by next generation sequencing (NGS) per IMWG (2016).

For analysis purposes, subjects in the All Treated population without MRD assessment will be considered as having positive MRD.

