2. SUMMARY OF KEY PROTOCOL INFORMATION

2.1. Changes to the Protocol Defined Statistical Analysis Plan

There were no changes or deviations to the originally planned statistical analysis specified in the protocol amendment 4 GSK Document Number [TMF-14344600](#) (Dated: 21/FEB/2022).

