2.2. Study Objective(s) and Endpoint(s)

Part 1: Dose Escalation

Objectives	Endpoints
Primary Objectives	Primary Endpoints

 To determine safety, tolerability and to establish the recommended Phase 2 dose (RP2D) of the combination of belantamab mafodotin and pembrolizumab in subjects with RRMM 	
 Percent of subjects with adverse events (AEs), changes in clinical signs and laboratory parameters Number of subjects with dose limiting toxicities (DLTs)
Secondary Objectives	Secondary Endpoints

 To evaluate clinical activity of the combination of belantamab mafodotin and pembrolizumab in subjects with RRMM 	
 Overall Response Rate (ORR), defined as the percentage of subjects with a confirmed partial response (PR) or better (i.e., PR, very good partial response [VGPR], complete response [CR] and stringent complete response [sCR]), according to the International Myeloma Working Group (IMWG) Response Criteria [Kumar, 2016].

 To evaluate the pharmacokinetic profile of belantamab mafodotin when administered intravenously in combination with pembrolizumab¹ 	
 Pharmacokinetic (PK) parameters following IV administration as data permit.

 To assess anti-drug antibodies (ADAs) against belantamab mafodotin¹ 	
 Incidence and titers of ADAs against belantamab mafodotin
Exploratory Objectives	Exploratory Endpoints

 To assess Minimal Residual Disease (MRD) in participants who achieve \geqVGPR or better 	
 Minimal Residual Disease (MRD) negativity rate, defined as: the percentage of subjects who are MRD negative in subjects who achieve VGPR or CR

 To characterize the relationship between clinical response and other biologic characteristics 	
 BCMA expression levels on malignant cells, serum sBCMA levels, serum cytokines, and immune cell characterization and their relationship to clinical response (Protein, RNA, DNA analysis)

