7.1.2.2. Summary Measure

MRD Negativity Rate

MRD negativity rate at any timepoint will be summarized. the number and percentage of participants who have achieved MRD negativity will be summarized by dose level. The corresponding 95% exact CI will be provided. Information of MRD will be included in the listing of response. For analysis purposes, subjects in the All Treated population without MRD assessment will be considered as having positive MRD.

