7.1.2.3. Population of Interest

The MRD negative rate analyses will be based on the All Treated population, unless otherwise specified.

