2.003	All Treated	See programming notes	Summary of MRD Negativity Rate by Investigator Assessed Best Response	
Report for: Part 1, Part 2, and combined Part 1 and Part 2; Summarize by: dose level (Refer to Section 5.1 for ordering of dose level and omit 1.92 mg/kg if data is not available). MRD negativity will be based on test result with sensitivity of 10^5. Refer to mid205678 (primary_01) Table 2.0040 for guidance. Include the following footnote:
 
Note: Minimal Residual Disease (MRD) negativity rate is defined as: the percentage of participants who are MRD negative by Next Generation Sequencing (NGS). Subjects without MRD assessment
	P-SAC [3], F-SAC [4]

Efficacy: Tables					
No.	Population	IDSL / Example Shell	Title	Programming Notes	Deliverable [Priority]
				will be considered as having positive MRD."	
Time-to-Event Endpoints					
2.004	All Treated	TTE1	Summary of Duration of Response by Investigator (IMWG 2016) (GSK2857916 2.5 mg/kg)	Report for: 2.5 mg/kg doses only; Refer to Section 5.1 and use only code A, code D, and code H for dose level	HDL [2], P-SAC [3], F-SAC [4]
2.005	All Treated	TTE1	Summary of Time to Response by Investigator (IMWG 2016) (GSK2857916 2.5 mg/kg)	Report for: 2.5 mg/kg doses only; Refer to Section 5.1 and use only code A, code D, and code H for dose level	P-SAC [3], F-SAC [4]
2.006	All Treated	TTE1	Summary of Time to Best Response by Investigator (IMWG 2016) (GSK2857916 2.5 mg/kg)	Report for: 2.5 mg/kg doses only; Refer to Section 5.1 and use only code A, code D, and code H for dose level	P-SAC [3], F-SAC [4]
2.007	All Treated	TTE1	Summary of Progression Free Survival by Investigator (IMWG 2016) (GSK2857916 2.5 mg/kg)	Report for: 2.5 mg/kg doses only; Refer to Section 5.1 and use only code A, code D, and code H for dose level; use mid205678(primary_01) T2.0080 for guidance	HDL [2], P-SAC [3], F-SAC [4]
2.008	All Treated	TTE1	Summary of Time to Progression by Investigator (IMWG 2016) (GSK2857916 2.5 mg/kg)	Report for: 2.5 mg/kg doses only; Refer to Section 5.1 and use only code A, code D, and code H for	P-SAC [3], F-SAC [4]

Efficacy: Tables					
No.	Population	IDSL / Example Shell	Title	Programming Notes	Deliverable [Priority]
				dose level	
2.009	All Treated	TTE1	Summary of Overall Survival (GSK2857916 2.5 mg/kg)	Report for: 2.5 mg/kg doses only; Refer to Section 5.1 and use only code A, code D, and code H for dose level; use mid205678(primary_01) T2.0150 for guidance	P-SAC [3], F-SAC [4]

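### The exploratory MRD negativity rate is a rate among VGPR/CR subjects in SAP Section 2.2 but a rate among all treated subjects in Section 7, with the response condition and sCR handled inconsistently

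*SAP*

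**What the plan says.** The SAP describes the MRD negativity rate in four places.

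- **Section 2.2, endpoint tables for Parts 1 and 2:** "the percentage of subjects who are MRD negative in subjects who achieve VGPR or CR". The objective beside it concerns participants with VGPR or better.
- **Section 7.1.2.1:** "the percentage of participants who are MRD negative (with threshold 10^{-5}) and achieve confirmed VGPR or CR from treatment start date", up to progression or new anti-cancer therapy. It adds that "subjects in the All Treated population without MRD assessment will be considered as having positive MRD". Section 7.1.2.3 sets the population: "The MRD negative rate analyses will be based on the All Treated population, unless otherwise specified". For Part 2, Sections 7.2.3.1 and 7.2.3.2 refer back to this definition and its summary measure, and 7.2.3.3 repeats the population.
- **Section 7.1.2.2, summary measure:** "the number and percentage of participants who have achieved MRD negativity will be summarized by dose level", with an exact 95% CI. No response condition is stated, and untested subjects again count as positive.
- **Section 16.11.5, Table 2.003:** the population is All Treated and the footnote defines the rate as "the percentage of participants who are MRD negative by Next Generation Sequencing (NGS"), again with no response condition. The title is "Summary of MRD Negativity Rate by Investigator Assessed Best Response".

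No section says which wording governs.

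**The concern.** Section 2.2 describes a conditional rate: depth of response among those who already responded deeply. Section 7 describes a joint rate over everyone treated. These answer different questions. A reader who takes the definition from Section 2.2 and the figure from Table 2.003 would read a rate in all treated subjects as a rate among deep responders.

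There are two smaller problems. The response condition in 7.1.2.1 is absent from 7.1.2.2 and from the footnote, so the numerator is not fixed either. And the definitions in 2.2 and 7.1.2.1 name VGPR and CR but not sCR. Section 7.1.1.1 ranks sCR as a separate category above CR, and Section 7.3.1 lists it explicitly when defining the rate of VGPR or better.

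What is at stake is the size and meaning of a reported percentage and its interval. No hypothesis, error rate, stopping rule or sample size depends on it.

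**Working it through.** The SAP states no expected MRD rate or precision, so there is no figure of its own to reproduce. The definitions can be compared algebraically.

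**Inputs**
- N = 28 (Section 2.3, Part 2; also the maximum in Section 3.1.2.1).
- V = number with confirmed VGPR or better. The SAP does not give it; assumed range about 15% to 60% of N. The upper end is the design alternative for ORR (Section 2.4.2), since at a given ORR the VGPR-or-better rate cannot be higher.
- a = MRD-negative subjects with confirmed VGPR or better. Assumed to be about half of V, for illustration only.
- b = MRD-negative subjects below VGPR. Assumed 0, 1 or 2.

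**Formulas**
- Section 2.2: R1 = a / V
- Section 7.1.2.1: R2 = a / N
- Section 7.1.2.2 and Table 2.003 footnote: R3 = (a + b) / N
- R1 / R2 = N / V, whatever a is. R3 / R2 = 1 + b / a.

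The first ratio assumes that both rates use confirmed response and count untested subjects as positive.

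**R1 against R2, N = 28, with exact (Clopper-Pearson) 95% CIs**

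| V (share of 28) | a | R1 = a/V (95% CI) | R2 = a/28 (95% CI) | Ratio 28/V |
|---|---|---|---|---|
| 4 (14%) | 2 | 50.0% (6.8–93.2) | 7.1% (0.9–23.5) | 7.0 |
| 6 (21%) | 3 | 50.0% (11.8–88.2) | 10.7% (2.3–28.2) | 4.7 |
| 8 (29%) | 4 | 50.0% (15.7–84.3) | 14.3% (4.0–32.7) | 3.5 |
| 14 (50%) | 7 | 50.0% (23.0–77.0) | 25.0% (10.7–44.9) | 2.0 |
| 17 (61%) | 8 | 47.1% (23.0–72.2) | 28.6% (13.2–48.7) | 1.65 |

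At exactly 60% the ratio is 1 / 0.60 = 1.67. A VGPR-or-better rate above 60% would need an ORR above the design alternative, and the gap would then narrow: 22 of 28 gives 28/22 = 1.27.

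**R3 against R2, a = 4**
- b = 0: both 4/28 = 14.3%.
- b = 1: 5/28 = 17.9% against 14.3%, ratio 1.25.
- b = 2: 6/28 = 21.4% against 14.3%, ratio 1.5.

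**sCR.** Section 7.1.2.1 asks that the subject achieve confirmed VGPR or CR; it does not ask that best response equal one of them. Under Table 4, VGPR followed by sCR is a confirmed VGPR (row 5), and CR followed by sCR is a confirmed CR (row 3). A subject who deepens through such a step still qualifies. A subject whose qualifying assessments are all sCR (row 1) does not, if the text is read literally. Suppose V = 8, a = 4, and 2 of the 4 are such subjects. Then R2 falls from 4/28 = 14.3% to 2/28 = 7.1%. If those two also leave the Section 2.2 denominator, R1 falls from 4/8 = 50.0% to 2/6 = 33.3%.

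**The case against.** The best defence is that the operational text agrees on the denominator. Sections 7.1.2, 7.2.3 and Table 2.003 all use All Treated, and 7.1.2.1, 7.1.2.2 and the footnote all count untested subjects as positive. That choice is conservative and avoids conditioning on a post-baseline outcome. Only Section 2.2 differs. A reader may also be able to rebuild the conditional rate: Table 2.003 is laid out by best response, Table 2.001 gives the VGPR-or-better rate in the same population, and Listing 1.0013 carries MRD by subject.

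Much of this stands. All Treated is a sound denominator, and nothing requires the responder-based rate to become the main one. But Section 2.2 still names a different quantity, and a rate rebuilt from other outputs is not a pre-specified one with its own interval.

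Four stronger readings are tempting and not supported:
- **Three definitions that all differ several-fold.** The large gap is between Section 2.2 and the rest. The 7.1.2.1 and footnote versions coincide unless an MRD-negative subject is below VGPR.
- **MRD-negative sCR subjects generally count as failures.** Table 4 rows 3 and 5 keep those who reach sCR through a confirmed VGPR or CR, and the footnote has no response condition at all. With the objective worded as VGPR or better, the omission looks like a slip.
- **Section 2.1 is false in saying** "There were no changes or deviations to the originally planned statistical analysis specified in the protocol amendment 4". That cannot be judged without the protocol.
- **The sensitivity of 10^5 in the Table 2.003 note is an error.** A minus sign may have been lost when the PDF was read; Section 7.1.2.1 gives the threshold as 10^-5.

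**Conclusion.** The inconsistency is real within the SAP. The analysis as written does not estimate the MRD endpoint stated in Section 2.2. The two denominators change the reported rate by N/V: for N = 28, about 1.7-fold at a VGPR-or-better rate of 60%, 2-fold at 50%, and 3.5- to 7-fold at about 30% down to 15%. Those rates are assumptions, so the size is a range and not a prediction. The missing response condition matters only if an MRD-negative subject is below VGPR. The missing sCR matters only for subjects whose sole qualifying confirmed response is sCR. Because the endpoint is exploratory and descriptive, the consequence is a mislabelled or ambiguous percentage, not an invalid test or decision.

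**What to change.** Define the numerator once: MRD negative at 10^-5 by NGS with confirmed VGPR, CR or sCR. Use that wording in Sections 2.2, 7.1.2 and 7.2.3 and in the Table 2.003 footnote.

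Report it in two labelled rows of Table 2.003, each with its exact 95% CI:
1. over All Treated, with untested subjects counted as positive, as Section 7 already specifies;
2. over subjects with confirmed VGPR or better, with untested subjects also counted as positive.

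The cost is a wording change in the SAP and one extra table row. No new data are needed.

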7.1.2.2. Summary Measure

MRD Negativity Rate

MRD negativity rate at any timepoint will be summarized. the number and percentage of participants who have achieved MRD negativity will be summarized by dose level. The corresponding 95% exact CI will be provided. Information of MRD will be included in the listing of response. For analysis purposes, subjects in the All Treated population without MRD assessment will be considered as having positive MRD.

7.1.2.3. Population of Interest

The MRD negative rate analyses will be based on the All Treated population, unless otherwise specified.

7.1.2.4. Statistical Analyses / Methods

Details of the planned displays are provided in [Appendix 11: List of Data Display](#), based on GSK data standards.

Unless otherwise specified, endpoints / variables defined in Section [7.1.2.1](#) will be summarised using descriptive statistics, graphically presented (where appropriate) and listed.

7.2. Part 2: Dose Expansion

7.2.1. Primary Efficacy Analyses

7.2.1.1. Endpoint / Variables

BOR

The definition of BOR is provided in Section [7.1.1.1](#). Details on derivation of confirmed response are provided in [Table 4](#).

ORR

The definition of ORR is provided in Section [7.1.1.1](#). Details on derivation of confirmed response are provided in [Table 4](#).

7.2.1.2. Summary Measure

ORR

The summary measure of ORR is provided in Section [7.1.1.2](#).

7.2.1.3. Population of Interest

At futility interim, the primary efficacy analysis of ORR will be based on the All Evaluable population.

Otherwise, the primary efficacy analysis of ORR will be based on the All Treated population, unless otherwise specified.

7.2.1.4. Statistical Analyses / Methods

Details of the planned displays are provided in [Appendix 11: List of Data Displays](#) and will be based on GSK data standards and statistical principles.

Unless otherwise specified, endpoints / variables defined in Section 7.2.1.1 will be summarised using descriptive statistics, graphically presented (where appropriate) and listed.

7.2.2. Secondary Efficacy Analyses

7.2.2.1. Endpoint / Variables

CBR

Clinical Benefit Rate (CBR), defined as the percentage of participants with a confirmed MR or better (i.e., MR, PR, VGPR, CR and sCR) as the BOR assessed by the investigator per IMWG (2016).

DOR

Duration of response (DoR), defined as the interval of time (in months) from first documented evidence of confirmed PR or better to the time when disease progression is documented assessed by the investigator per IMWG (2016), or death due to PD among participants with a confirmed PR or better as the BOR. Responders without confirmed PD will be censored at the censoring time point for time to progression as specified in [Table 6](#).

TTR

Time to response (TTR), defined as the interval of time (in months) between the date of first dose and the first documented evidence of response (PR or better) among participants with a confirmed PR or better as the BOR assessed by the investigator per IMWG (2016).

TTBR

Time to best response (TTBR), defined as the interval of time (in months) between the date of first dose and the earliest date of achieving BOR among participants with a confirmed PR or better as the BOR assessed by investigator per IMWG (2016).

PFS

Progression-free survival (PFS), defined as the interval of time (in months) from first dose until the earlier date of disease progression per IMWG (2016), or the date of death due to any cause. Determination of dates of PFS events and dates for censoring are described in [Table 5](#).

TTP

Time to disease progression (TTP), defined as the interval of time (in months) from first dose until the earlier date of PD per IMWG (2016), or the date of death due to PD. Determination of dates of TTP events and dates for censoring are described in [Table 6](#).

OS

Overall Survival (OS), defined as the interval of time (in months) from first dose to the date of death due to any cause. Participants who withdraw consent from the study or are lost to follow-up will be censored at the time of withdrawal or lost to follow-up. Participants who do not have a death record at the clinical cut-off date for the analysis will be censored at the last known alive date. The last contact date will be determined by

the maximum collection/assessment date from among selected data domains within the clinical database.

Table 5 Assignments of Progression and Censoring Dates for PFS Analysis

Situation	Date of Event (Progression/Death) or Censored ¹	Event (Progression/Death) Or Censored
No adequate baseline assessments ⁴ and the subject has not died (if the subject has died follow the rules for death indicated at the bottom of the Table)	First dose	Censored
No post-baseline assessments and the subject has not died (if the subject has died follow the rules for death indicated at the bottom of the Table)	First dose	Censored
Progression documented between scheduled visits	Date of assessment of progression	Event
With post-baseline assessment but no progression (or death)	Date of last 'adequate' assessment of response ²	Censored
No adequate post-baseline assessment before start of new anticancer therapy	First dose	Censored
With adequate post-baseline assessment and new anticancer treatment started (prior to documented disease progression). ³	Date of last 'adequate' assessment of response ² (on or prior to starting anti-cancer therapy)	Censored
Death before first scheduled assessment (or Death at baseline or without any adequate assessments)	Date of death	Event
Death between adequate assessment visits	Date of death	Event
Death or progression after more than three missed scheduled assessment	Date of last 'adequate' assessment of response ² (prior to missed assessments): If the disease assessment is every 3 weeks, a window of 66 days (9 weeks + 3 day window) will be used to determine whether there is extended time without adequate assessment. If the time difference between PD/death and last adequate disease assessment is more than 66 days, PFS will be censored at the last adequate disease assessment prior to PD/death.	Censored

¹ Event or censored are based on confirmed responses.

² An adequate assessment is defined as an unconfirmed assessment where the investigator assessed response is sCR, CR, PR, VGPR, MR, or SD.

³ If PD and New anti-cancer therapy occur on the same day assume the progression was documented first e.g., outcome is progression and the date is the date of the assessment of progression).

⁴ Adequate baseline assessment is defined as at baseline, a patient has at least one of the following measurements: a. Serum M-protein ≥ 0.5 g/dL (≥ 5 g/L) or b. Urine M-protein ≥ 200 mg/24h or c. Serum FLC assay: Involved FLC level ≥ 10 mg/dL (≥ 100 mg/L) and an abnormal serum free light chain ratio (< 0.26 or > 1.65).

Table 6 Assignments for Progression and Censoring Dates for TTP Analysis

Situation	Date of Event (Progression/Death due to PD) or Censored ¹	Event (Progression/Death due to PD) Or Censored
No adequate baseline assessments ⁴ and the subject has not died (if the subject has died due to PD follow the rules for death indicated at the bottom of the Table)	First dose	Censored
No post-baseline assessments and the subject has not died (if the subject has died due to PD follow the rules for death due to PD indicated at the bottom of the Table)	First dose	Censored
Progression documented between scheduled visits	Date of assessment of progression	Event
With post-baseline assessment but no progression (or death due to PD)	Date of last 'adequate' assessment of response ²	Censored
No adequate post-baseline assessment before start of new anticancer therapy	First dose	Censored
With adequate post-baseline assessment and new anticancer treatment started (prior to documented disease progression). ³	Date of last 'adequate' assessment of response ² (on or prior to starting anti-cancer therapy)	Censored
Death due to PD before first scheduled assessment (or Death at baseline or without any adequate assessments)	Date of death	Event
Death due to PD between adequate assessment visits	Date of death	Event
Death from causes other than PD before first scheduled assessment (or Death at baseline or without any adequate assessments)	Date of death	Censored
Death from causes other than PD between adequate assessment visits	Date of death	Censored
Death due to PD or progression after more than three missed scheduled assessment	Date of last 'adequate' assessment of response ² (prior to missed assessments): If the disease assessment is every 3 weeks, a window of 66 days (9 weeks + 3 day window) will be used to determine whether there is extended time without adequate assessment. If the time difference between PD/death due to PD and last adequate disease assessment is	Censored

CONFIDENTIAL

205207

Situation	Date of Event (Progression/Death due to PD) or Censored ¹	Event (Progression/Death due to PD) Or Censored
	more than 66 days, PFS will be censored at the last adequate disease assessment prior to PD/death due to PD.	

¹ Event or censored are based on confirmed responses.

² An adequate assessment is defined as an assessment where the investigator assessed response is sCR, CR, PR, VGPR, MR, or SD .

³ If PD and New anti-cancer therapy occur on the same day assume the progression was documented first e.g., outcome is progression and the date is the date of the assessment of progression).

⁴ Adequate baseline assessment is defined as at baseline, a patient has at least one of the following measurements: a. Serum M-protein ≥ 0.5 g/dL (≥ 5 g/L) or b. Urine M-protein ≥ 200 mg/24h or c. Serum FLC assay: Involved FLC level ≥ 10 mg/dL (≥ 100 mg/L) and an abnormal serum free light chain ratio (< 0.26 or > 1.65).

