11	sCR/CR/VGPR/PR/MR	PD (any reason) OR No subsequent disease assessment: subject died or discontinued study or started new anti-cancer therapy before further adequate disease assessment	SD
12	sCR/CR/VGPR/PR/MR/PD (due to reasons other than imaging, i.e., plasmacytoma or bone lesion)	No subsequent disease assessment: subject has not died, discontinued from study or (except for PD) started new anti-cancer therapy; but as yet has no further adequate disease assessments	Unconfirmed sCR/CR/VGPR/PR/MR/PD Will be categorized as NE for ORR analysis. For ORR analysis in IA, the UC response (PR or better) will be counted as responder.
13	PD (due to reasons other than imaging, i.e., plasmacytoma or bone lesion)	PD (any reason) including PD after initiation of new anti-cancer therapy OR	PD

	Response at the First Time Point	Response at Subsequent Time Point¹	Confirmed Response at the First Time Point
		No subsequent disease assessment: subject died due to PD before further adequate disease assessment (including death due to PD after initiation of new anti-cancer therapy)	
14	PD (due to reasons other than imaging, i.e., plasmacytoma or bone lesion)	sCR/CR/VGPR/PR/MR/SD OR No subsequent disease assessment: subject died due to reasons other than PD before further adequate disease assessment OR No subsequent disease assessment: subject discontinued study before further adequate disease assessment	NE
15	SD	Any OR No subsequent disease assessment	SD
16	PD due to imaging (plasmacytoma or bone lesion)	Any OR No subsequent disease assessment	PD
17	NE or missing	Any OR No subsequent disease assessment	NE

1 Subsequent disease assessment is defined as the next adequate (not missing or NE) disease assessment following the first timepoint before (or on the same date of) start of new anti-cancer therapy except for confirmation of PD, for which PD or death due to PD after new anti-cancer therapy are considered for confirmation of PD. No minimal time interval is required for the subsequent disease assessment but a different sample is required for confirmation.

2 SD does not need to be confirmed.

3 PD due to imaging (i.e., plasmacytoma or bone lesion) does not need to be confirmed.

Where criteria are not mutually exclusive, take the first that applies.

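### The duration-of-response rule applies Table 6 only to responders without confirmed PD, so a late PD that TTP and PFS censor counts, read literally, as a DoR event

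*SAP*

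**What the plan says.** All of the following stands in SAP Section 7.2.2.1 unless noted.

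- **PFS and TTP.** Each is sent to its table for events and censoring alike: "Determination of dates of PFS events and dates for censoring are described in" Table 5, and "Determination of dates of TTP events and dates for censoring are described in" Table 6.
- **DoR.** The interval runs "from first documented evidence of confirmed PR or better to the time when disease progression is documented assessed by the investigator", or to death due to PD. No exception is made for intervening therapy or missed assessments. The only link to a table is the next sentence: "Responders without confirmed PD will be censored at the censoring time point for time to progression", with a reference to Table 6.
- **New therapy before PD.** Both tables have the row "With adequate post-baseline assessment and new anticancer treatment started (prior to documented disease progression" and censor at the last adequate assessment on or before the start of that therapy.
- **Long gap before PD.** Table 6 has "Death due to PD or progression after more than three missed scheduled assessment" and Table 5 has "Death or progression after more than three missed scheduled assessment". Both censor at the last adequate assessment, using a 66-day window when assessments are three-weekly.
- **Confirmation.** Table 4, footnote 1 (Section 7.1.1.1) restricts subsequent assessments to those before new therapy, except for confirming PD, "for which PD or death due to PD after new anti-cancer therapy are considered for confirmation of PD".
- **Displays.** Appendix 11 lists DoR (Table 2.004) and PFS (Table 2.007) among the headline results.

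**The concern.** DoR and TTP have the same events, PD and death due to PD, and differ only in where the clock starts. They should therefore share one set of dating rules. The DoR sentence instead sorts patients by whether confirmed PD was ever recorded. Those without it get the Table 6 censoring date. Those with it fall outside the sentence and are events on the PD date, even where Table 6 would censor them.

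Three things are at stake. First, the same patient may be a DoR event and a PFS and TTP censored case, with a DoR longer than the PFS time, in two headline tables. Second, censoring at a gap or a switch of therapy comes to depend on what happens afterwards, and Kaplan-Meier estimation does not allow for that. Third, the definition and the following sentence disagree on a responder who dies of PD between adequate assessments with no confirmed PD: the definition makes this an event, while the patient is also literally without confirmed PD.

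**Working it through.** **1. The plan's own window.** 9 weeks × 7 + 3 days = 66 days, as Tables 5 and 6 state. The gap row therefore applies from a gap of 67 days.

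**2. Formulas for one responder.** Let F be first dose (Day 1), R the first confirmed response, L the last adequate assessment and P the confirmed PD, where P falls under a Table 6 censoring row.

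- PFS and TTP time (censored) = L − F + 1
- DoR as written (event) = P − R + 1
- DoR if dated by Table 6 (censored) = L − R + 1

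DoR as written exceeds the PFS time when P − R + 1 > L − F + 1, that is, when P − L > R − F: the gap is longer than the time to response.

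**3. Examples.** All dates are assumed, with L = Day 127.

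| Case | R | P | PFS/TTP, censored | DoR as written, event | DoR by Table 6, censored |
|---|---|---|---|---|---|
| Gap of 67 days | 43 | 194 | 127 d | 194 − 43 + 1 = 152 d | 127 − 43 + 1 = 85 d |
| New therapy about Day 135 | 43 | 300 | 127 d | 300 − 43 + 1 = 258 d | 85 d |
| Gap of 67 days, late response | 85 | 194 | 127 d | 194 − 85 + 1 = 110 d | 127 − 85 + 1 = 43 d |

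The first two rows meet the condition (67 > 42 and 173 > 42). The third does not (67 < 84), and there DoR is shorter than the PFS time. Since the shortest qualifying gap is 67 days, every gap-row responder with a time to response below 67 days has DoR above the PFS time. Dated by Table 6, DoR cannot exceed TTP, because both end at the same date and R is not before F.

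**4. Group level.** This is a large-sample simulation of the new-therapy case; none of its inputs is in the SAP. Assumed: exponential time to PD with median 8 months from response; 30% of responders assigned a switch time uniform on 1 to 8 months, effective if PD has not yet occurred; median 16 months to PD after the switch; data cut-off uniform on 14 to 24 months; the last adequate assessment taken as the switch time. The share still PD-free at the assigned switch is (8/ln 2)/7 × (2^(−1/8) − 2^(−1)) = 1.649 × 0.417 = 0.688, so about 0.30 × 0.688 = 21% of responders actually switch before PD.

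| Rule | Median DoR | 12-month DoR |
|---|---|---|
| Table 6 for all | 8.0 months | 35.3% |
| As written (PD seen later is an event, otherwise censored at the switch) | 7.9 months | 34.0% |
| As written, median after the switch also 8 months | 7.7 months | 32.3% |

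In the last row the hazard of PD is the same before and after the switch, so a valid analysis would show no difference. The downward shift comes from the rule alone: switchers with a later PD stay in the risk set and supply events, while switchers without one are removed at the switch.

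**5. Death due to PD.** Table 6 makes a PD death between adequate assessments an event on the date of death, so it holds no censoring date for the DoR sentence to use. The conflict is confined to responders with no earlier PD assessment, since Table 4 row 13 already treats a PD death after a first non-imaging PD as confirmed PD.

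**The case against.** The strongest reply is that the intent is plain. DoR shares its events with TTP, Table 6 is its only dating reference, and a sensible programmer would apply that table throughout. The intent is probably as described, but the text limits the reference to one group and to censoring, so two programmers could produce different results from it.

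For new therapy there is a textual defence. Section 7.1.1.1 ends the BOR period at new therapy, and under ORR it limits the assessments considered to those before confirmed PD or new therapy. DoR is defined among responders by BOR. If that cut-off is read across, PD first seen after a switch is never used. This stands in part: the sentence sits under ORR and is not carried to DoR, but it makes this half of the point the weaker one. It says nothing about long gaps.

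Some stronger readings should be resisted.

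- A reader might infer from Table 4, footnote 1 that the plan expects a first PD after new therapy to be a DoR event. The footnote concerns later data that confirm a PD, with the confirmed response assigned to the first time point.
- A reader might infer that the rule inflates the DoR curve. Individual times are lengthened, but under the literal rule the simulated curve falls.
- A reader might infer that Table 6 never dates a PD death as censored. Its last row does, after missed assessments.

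It is also fair that DoR is a descriptive secondary endpoint, summarised only if events suffice, and that Section 7.2.2.2 plans the median and quartiles for DoR but no 12-month rate.

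**Conclusion.** The point holds as a drafting defect with a real analytical consequence, firmly for PD more than 66 days after the last adequate assessment and less firmly for PD first seen after new therapy. For such patients the literal DoR rule contradicts the TTP and PFS rules. It gives a DoR longer than the PFS time whenever the gap exceeds the time to response, which is common for early responders but not automatic. The comparison is of an event time with a censored time, so it shows inconsistent rules and not by itself a biased summary.

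The bias comes from outcome-dependent censoring. Under the assumed inputs it is small and downward, about 0.1 month in the median, or about 0.3 month with equal medians before and after the switch. The long-gap case was not simulated. The number of patients affected cannot be derived from the SAP. With about 28 subjects in Part 2 and an ORR of 40% to 60%, there would be about 11 to 17 responders in that part (28 × 0.4 = 11.2; 28 × 0.6 = 16.8), so one or two reclassified patients could still move the reported median. The correction should be made because DoR is a headline display, but the primary endpoint is untouched.

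**What to change.** Replace the DoR censoring sentence in Section 7.2.2.1 by:

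*DoR event and censoring dates follow Table 6 for all responders, including the new-therapy, missed-assessment and death-due-to-PD rows, with time counted from the first documented confirmed PR or better. Where Table 6 would give a censoring date before the response date (the First dose rows), the responder is censored at the response date.*

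The second part is needed because a responder without an adequate baseline would otherwise be censored at first dose, before the response began. The cost is the rewording of one SAP sentence and a matching check of the DoR program behind Table 2.004, Figure 2.003 and Listing 1.0014. No new data or displays are needed. If DoR was already programmed to follow Table 6 throughout, results change only for a responder caught by the First dose rule.
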